5.2. Selection of Instruments

We selected instruments based on our prior studies and the theoretical framework of our intervention, which seeks to improve patients' QOL, illness understanding, use of adaptive coping strategies and ultimately communication and delivery of EOL care. Study staff will administer study assessments at baseline and multiple follow-up time points (with a +/- two-week window) to accommodate patient schedules (see Table 1). The selected self-report measures have strong psychometric properties and have been well validated in previous studies. All study measures are available in both English and Spanish, except the Self-Administered Comorbidity Questionnaire and the Prognosis and Treatment Perceptions Questionnaire, which were translated (forward and backward) into Spanish with a native Spanish speaking clinician.

Measures:

Demographic Questionnaire: Participants will self-report their gender, race/ethnicity, marital status, religion, education level, employment status, tobacco use, travel time and transportation mode to the cancer center, and health insurance co-payment charge.

Self-Administered Comorbidity Questionnaire (SCQ): Medical comorbidity will be assessed at baseline with the Self-Administered Comorbidity Questionnaire.⁴⁵ Patients will report on the presence of twelve comorbidities such as heart disease, lung disease, diabetes and arthritis. They will also have the option of reporting up to three further unlisted comorbidities and will be assigned a comorbidity score ranging from 0-45.

Functional Assessment of Cancer Therapy-Lung (FACT-L): The FACT-L is a 35-item QOL tool that assesses physical, social/family, emotional, and functional well-being, as well as lung cancer specific symptoms over the past 7 days.⁴⁶ We have used this measure in three prior PC trials in patients with lung cancer, demonstrating that early involvement of PC improves FACT-L scores.^{6,10}

EuroQol-5 Dimension (EQ-5D): The EQ-5D measures five dimensions of health (mobility, self-care, usual activities, pain/discomfort, and anxiety/depression) with three levels of severity and self-rated health status on a 0-100 visual analog scale^{47,48} and is sensitive to QOL changes in patients with lung cancer.^{47,49}

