7.4. Sample Size and Power Calculation

The primary endpoint of the study is to establish that stepped PC is non-inferior to early integrated PC in the change in QOL, as measured by the FACT-L at week-24. Although the primary endpoints in our previous studies assessed the change in FACT-L from baseline to week-12, we chose to focus on QOL at 24 weeks as the life-expectancy of patients with advanced lung cancer has improved over the last few years. Thus, examining QOL at 12 weeks may overlook important differences between groups as the disease progresses. In our most recent trial of early integrated PC versus standard oncology care, we observed a 7.5-point difference in the FACT-L at week-24 favoring the integrated PC group. Thus, we chose a conservative non-inferiority margin of 4.5 points, which is slightly less than 50% of the previously observed advantage with early integrated PC compared to oncology care alone. As a 6-point difference in FACT-L score is considered the lowest range of a clinically meaningful difference, our non-inferiority margin would not reach the threshold of clinically meaningful difference in QOL.⁵⁵ With

188 patients per group, we will have >80% power to establish the non-inferiority of stepped PC compared to early integrated PC on the FACT-L with a one-sided alpha of 0.05, and a non-inferiority margin of 4.5 points. We are currently observing 35% missing data across sites at 24 weeks, primarily due to progressive illness or death. Therefore, we increased our sample size to 255 per group to ensure we have adequate power to assess for non-inferiority of stepped PC.

Our study also has adequate power to assess for non-inferiority of stepped PC compared to early integrated PC in EOL communication and hospice length-of-stay. With a sample size of 510, we will have >80% power, with a one-sided alpha of 0.05, to reject the hypothesis that patient-reported EOL communication with stepped PC would be 10% lower than early integrated PC, assuming that the rate of EOL communication in the early integrated PC group is 30% (based on our recent trial). With this sample size, we will also have >80% power to establish the non-inferiority of stepped PC compared to early integrated PC in hospice length-of-stay with a one-sided alpha of 0.05, and a non-inferiority margin of 7 days. We were conservative with our power estimations by using the highest observed standard deviation for all outcomes from prior studies.

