## 7. Sample Size

Sample size calculations were performed to detect a non-inferiority margin of 4.5 points on the FACT-L at week 24, assuming a standard deviation of 17.5 points and a between-group difference of 0 points. 188 patients per group were required to achieve 80% power with a one-sided significance level of 0.05. To account for an anticipated 36% rate of missing data at week 24 due to loss-to-follow-up, withdrawal, or death, enrollment of 255 per group (510 total) was planned.

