### *Missing Data*

Primary analyses will include available data without imputation of missing data. The characteristics of patients who complete versus do not the week 24 survey will be compared descriptively. Sensitivity analyses will explore how different assumptions about the missing data mechanisms affect estimated outcomes. These sensitivity analyses may include multiple imputation, terminal decline joint modeling, or partially conditional models, which provide estimates of the mean conditional on being alive and observed at each timepoint.

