## **9. Statistical Analysis**

### *Primary Outcome*

The primary outcome is patient-reported quality of life at week 24, as measured by the FACT-L. The difference in week 24 means between intervention groups will be estimated using a linear regression model with group assignment (stepped PC vs early integrated PC) and baseline FACT-L score, as well as randomization stratification factors, as main effects. Using the pre-specified non-inferiority margin of 4.5 points, non-inferiority of stepped PC will be established if the lower limit of the 90% confidence interval (CI) for the estimated difference in means is greater than -4.5. The corresponding p-value for non-inferiority will be calculated using a one-sided test of the estimated difference in means against a null value of -4.5 with a significance level of 0.05. Model-based estimates of the mean with 95% CI in each group, the difference in means between groups and its 90% CI, and the p-value will be reported.

To accompany the approach described above, we will also use a linear mixed effects regression model to estimate the difference in week 24 means between intervention groups. This model will utilize FACT-L scores at baseline, week 12, and week 24, with estimation via maximum likelihood. The model will include fixed effects for group assignment (stepped PC vs early integrated PC), time from baseline (in weeks), time-by-group interaction, and randomization stratification factors, as well as random intercepts for each patient. A contrast will be used to estimate the difference in means at week 24, and this estimate will be evaluated for non-inferiority in the same manner described above. This will be reported as a sensitivity analysis for evaluating non-inferiority for the primary outcome.

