#### *Exploratory Outcomes*

The rate of change in quality of life from baseline to week 48 (assessed by the FACT-L) will be compared between groups using a linear mixed effects regression model. This model will utilize FACT-L scores at each timepoint, with estimation via maximum likelihood. The model will include fixed effects for group assignment (stepped PC vs early integrated PC), time from baseline (in weeks), time-by-group interaction, and randomization stratification factors, as well as random intercepts for each patient.

Model-based estimates of the slope with 95% CI in each group and the difference in slopes between groups and its 95% CI will be reported.

The difference in means between intervention groups in patient-reported depression symptoms (assessed by PHQ-9) and coping strategies (assessed by subscales and higher-order factors of Brief Cope) at week 24, will be estimated for each outcome using a linear regression model with group assignment (stepped PC vs early integrated PC) and baseline score, as well as randomization stratification factors, as main effects. Model-based estimates of the mean with 95% CI in each group and the difference in means between groups and its 95% CI will be reported.

Rates of prognostic understanding at week 24, based on PTPQ items eliciting the patient's goal of cancer care ("to cure my cancer" vs any other option) and the patient's assessment of curability ("yes" vs "no") will be compared using generalized linear models specified with an identity link function and binomial response probability distribution. Model-based estimates of the rate with 95% CI in each group and the difference in rates between groups and its 95% CI will be reported.

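### The mixed-model sensitivity analysis for the primary outcome assumes straight-line change over weeks 0, 12 and 24, so its week-24 contrast is biased unless the group difference grows linearly or is zero at both visits; the primary test is unaffected.

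*SAP*

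**What the plan says.** The primary test in SAP section 9 is a linear regression of the week-24 FACT-L score on group, baseline score and the stratification factors. Non-inferiority requires the lower 90% confidence limit to exceed -4.5. This regression makes no use of week 12.

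A second model is then specified on the baseline, week-12 and week-24 scores. It is fitted by maximum likelihood with "fixed effects for group assignment (stepped PC vs early integrated PC), time from baseline (in weeks), time-by-group interaction", the stratification factors and a random intercept per patient. The SAP continues: "A contrast will be used to estimate the difference in means at week 24". The estimate is judged by the same non-inferiority rule, and its status is explicit: "This will be reported as a sensitivity analysis for evaluating non-inferiority for the primary outcome".

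The exploratory model for change to week 48 has the same fixed and random effects, and its output is "Model-based estimates of the slope with 95% CI in each group and the difference in slopes between groups". Time is therefore a single linear term. Neither the SAP nor its addendum adds a visit factor, a quadratic term or a spline.

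SAP section 7 expects substantial loss: "To account for an anticipated 36% rate of missing data at week 24". The Missing Data part of SAP section 8 plans further work: "Sensitivity analyses will explore how different assumptions about the missing data mechanisms affect estimated outcomes". The methods it names are optional examples.

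**The concern.** A model with one straight line per arm cannot reproduce three arbitrary visit means. Its fitted week-24 value draws on week 12 and baseline as well as week 24, so the contrast equals the week-24 difference only under conditions that the plan does not establish.

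The contrast will be read beside the primary result as a second estimate of the same quantity against the same margin. It departs from the primary regression in two ways at once: it brings in patients without a week-24 score, and it imposes linearity. The SAP does not say which of these it is meant to test, so agreement or disagreement has no single explanation. It is also the only supporting model for the primary outcome that the SAP specifies in full, in a trial expecting about a third of week-24 scores to be missing.

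**Working it through.** **Inputs from the documents.** Visits 0, 12 and 24; linear time; random intercepts; margin 4.5; one-sided 0.05 (SAP 9). SD 17.5, 255 per arm, 36% missing at week 24 (SAP 7).

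**Assumptions.** Correlation between visits of 0.3, 0.5 or 0.7 and the timing of dropout, neither of which the documents give. Dropout is monotone, alike in both arms and, for the weights, unrelated to outcome. The SD is constant over visits.

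**The plan's own figure.** n = 2 × 17.5² × (1.645 + 0.842)² / 4.5² = 187.0, rounded up to 188 per group, with power 80.2%. This agrees with SAP 7.

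**Weights, complete data.** Code the visits -1, 0, 1 and write d0, d12, d24 for the group differences. The fitted difference at the last visit is the mean plus the slope:

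(d0 + d12 + d24)/3 + (d24 − d0)/2 = −d0/6 + d12/3 + 5·d24/6.

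**Weights in general.** Any fit that reproduces a straight line needs weights summing to 1 and satisfying 12·w12 + 24·w24 = 24. With w12 = w, this gives w24 = 1 − w/2 and w0 = −w/2. Hence

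contrast = d24 + w × (d12 − (d0 + d24)/2).

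Randomisation makes the expected d0 zero, so the bias is w × (d12 − d24/2).

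Generalised least squares gives, at correlations 0.3 / 0.5 / 0.7:

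| Observed at week 12 / week 24 | w | SE of contrast |
|---|---|---|
| 100% / 100% | 0.333 / 0.333 / 0.333 | 1.46 / 1.48 / 1.51 |
| 64% / 64% | 0.310 / 0.282 / 0.254 | 1.81 / 1.79 / 1.73 |
| 80% / 64% | 0.405 / 0.396 / 0.385 | 1.75 / 1.73 / 1.68 |
| 100% / 64% | 0.506 / 0.519 / 0.528 | 1.69 / 1.66 / 1.62 |

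**Consequence at the margin.** With true d24 = -4.5, P(declared non-inferior) = Φ(bias/SE − 1.645). For example, with 80%/64% observed, correlation 0.5 and d12 = 0, the bias is 0.396 × 2.25 = 0.89, and Φ(0.89/1.73 − 1.645) = 0.13. Over the three 36%-missing rows:

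| True d12 | Contrast | P(declared non-inferior) |
|---|---|---|
| 0 (wholly late) | -3.3 to -3.9 | 9-18% |
| -1.5 | -4.1 to -4.3 | 6-8% |
| -2.25 (linear) | -4.5 | 5% |
| -4.5 (complete by week 12) | -5.1 to -5.7 | 1-2.4% |

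**Simulation check** (80%/64%, correlations 0.5-0.7, 2,500 trials per cell, no strata). With dropout completely at random, the planned model declared non-inferiority in 11.9-13.7% (late), 6.3-7.0% (d12 = -1.5), 4.4-4.7% (linear) and 1.7-2.0% (early). A categorical-visit model with a common baseline mean stayed at 4.2-5.8% throughout. Dropout depending on the last observed score gave a similar picture: 12.2-13.0% for the late case, and 4.3-5.5% for the categorical model in all cases.

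**Visit window.** Protocol 5.2 allows "multiple follow-up time points (with a +/- two-week window) to accommodate patient schedules". With actual times spread evenly over that window and a group difference that changes slope at week 12 (80%/64%, correlations 0.5-0.7), the late and early contrasts are still about -3.7 and -5.3. Using exact dates does not remove the bias.

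**Unequal dropout.** Each arm then has its own w, and curvature common to both arms no longer cancels. With 36% against 26% missing at week 24, correlation 0.5 and 5 points of shared curvature, about 0.14 points leak into the contrast even when d12 = d24/2.

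**Precision of alternatives** (80%/64%, correlations 0.3 / 0.5 / 0.7):

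| Model | SE |
|---|---|
| Planned linear | 1.75 / 1.73 / 1.68 |
| Categorical, separate baseline means | 1.90 / 1.83 / 1.74 |
| Categorical, common baseline mean | 1.84 / 1.66 / 1.36 |
| Primary regression | 1.85 / 1.68 / 1.38 |

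**The case against.** The strongest reply is that this model decides nothing and that its realistic error is small. Both parts stand. The primary regression alone carries the test. In the intermediate case the bias is about 0.2-0.4 points against an SE of about 1.6-1.8, while protocol 7.4 puts the smallest clinically meaningful difference at 6 points. Under the design assumption of no difference, a zero difference at both visits gives no bias. The extreme rates need a deficit exactly on the margin together with an extreme time course.

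A second reply is that linearity buys precision. Against recoding time alone, that is right: in the -1.5 case with 80%/64% observed, root mean squared error is 1.78/1.75/1.70 for the planned model and 1.90/1.83/1.74 for categorical visits with separate baseline means. The precision gain at moderate and high correlation comes from the baseline constraint, not from the time coding.

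A reader might also infer that the bias favours stepped PC, because protocol 7.4 says "examining QOL at 12 weeks may overlook important differences between groups as the disease progresses". The documents do not support that. The sentence fits a steadily growing difference, which gives no bias, as well as a late one, and an early deficit that levels off would be overstated.

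Finally, sensitivity analyses often relax several assumptions together. That is acceptable when the purpose is stated; here it is not.

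**Conclusion.** The point holds as a specification weakness in one sensitivity analysis. The contrast called the week-24 difference is a weighted mix of visits. In expectation its bias is w × (d12 − d24/2), with w = 1/3 for complete data and about 0.25-0.53 with 36% missing. With d24 at -4.5, the error rate runs from about 1% to 18% between the bounding time courses and is 6-8% in the intermediate case, against a nominal 5%. The direction is unknown.

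The ranges rest on assumed correlations and dropout timing. The formula requires similar dropout in the two arms; when dropout differs, a week-12 difference of half the week-24 difference is no longer enough to remove the bias. Dropout that depends on unobserved scores, and death as such, were not modelled.

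A reader might conclude that the non-inferiority decision itself is compromised. It is not: that decision rests on the primary regression, which does not use this model. The change is worth making because it is cheap and this is the supporting analysis readers will look to first.

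**What to change.** In SAP section 9, respecify this sensitivity analysis with visit (0, 12, 24) as a categorical factor, group-by-visit effects, a common baseline mean for the two arms (or baseline as a covariate), unstructured covariance and the stratification factors. Test the week-24 contrast against -4.5 as planned. Keep the baseline constraint in the change, since recoding time alone costs precision. State that the analysis is meant to examine the effect of including patients without a week-24 score.

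SAP version 1.0 is dated October 2023 and addendum entries run to January 2024, so the planned model may already have been run. If so, report the categorical version beside it through the addendum and label it as added after the SAP was finalised.

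The cost is one addendum entry and a few lines of code, with no new data. There are a few more mean and covariance parameters, which is minor with 510 patients. At low correlation precision falls slightly (SE 1.84 against 1.75 at 0.3). Visit categories ignore exact timing within the two-week window, as the primary regression already does.

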#### *Secondary Outcomes*

The difference between groups in the rate of patient-clinician communication about EOL care preference at the final follow-up assessment will be assessed using a generalized linear regression model specified with an identity link function and binomial response probability distribution. The model will include group assignment (stepped PC vs early integrated PC) and randomization stratification factors as main effects. Using the pre-specified non-inferiority margin of 10%, the nominal p-value for non-inferiority will be calculated using a one-sided test of the estimated difference in rates against a null value of -10%. Non-inferiority of stepped PC will be established if the nominal p-value is significant after application of the multiplicity adjustment procedure for secondary outcomes. Model-based estimates of the rate with 95% CI in each group, the difference in rates between groups and its 90% CI, the nominal p-value, and the multiplicity-adjusted p-value will be reported.

The difference between groups in the mean length of stay in hospice among patients who die during the study will be assessed using a linear regression model with main effects for group assignment (stepped PC vs early integrated PC) and randomization stratification factors. Using the pre-specified non-inferiority margin of 7 days, the nominal p-value for non-inferiority will be calculated using a one-sided test of the estimated difference in rates against a null value of -7. Non-inferiority of stepped PC will be established if the nominal p-value is significant after application of the multiplicity adjustment procedure for secondary outcomes. Model-based estimates of the mean with 95% CI in each group, the difference in means between groups and its 90% CI, the nominal p-value, and the multiplicity-adjusted p-value will be reported.

The difference between groups in the mean number of outpatient PC visits per patient will be assessed using a linear regression model with main effects for group assignment (stepped PC vs early integrated PC) and randomization stratification factors. Superiority of stepped PC will be established if the nominal p-value for the difference in means (against a null value of 0) is significant in favor of stepped PC after application of the multiplicity adjustment procedure for secondary outcomes. Model-based estimates of the mean with 95% CI in each group, the difference in means between groups and its 95% CI, and the nominal p-value, and the multiplicity-adjusted p-value will be reported.

#### *Exploratory Outcomes*

The rate of change in quality of life from baseline to week 48 (assessed by the FACT-L) will be compared between groups using a linear mixed effects regression model. This model will utilize FACT-L scores at each timepoint, with estimation via maximum likelihood. The model will include fixed effects for group assignment (stepped PC vs early integrated PC), time from baseline (in weeks), time-by-group interaction, and randomization stratification factors, as well as random intercepts for each patient.

Model-based estimates of the slope with 95% CI in each group and the difference in slopes between groups and its 95% CI will be reported.

The difference in means between intervention groups in patient-reported depression symptoms (assessed by PHQ-9) and coping strategies (assessed by subscales and higher-order factors of Brief Cope) at week 24, will be estimated for each outcome using a linear regression model with group assignment (stepped PC vs early integrated PC) and baseline score, as well as randomization stratification factors, as main effects. Model-based estimates of the mean with 95% CI in each group and the difference in means between groups and its 95% CI will be reported.

Rates of prognostic understanding at week 24, based on PTPQ items eliciting the patient's goal of cancer care ("to cure my cancer" vs any other option) and the patient's assessment of curability ("yes" vs "no") will be compared using generalized linear models specified with an identity link function and binomial response probability distribution. Model-based estimates of the rate with 95% CI in each group and the difference in rates between groups and its 95% CI will be reported.

Multiple metrics of healthcare utilization at the end of life will be compared between intervention groups among patients who die during the study. The number of emergency department visits and number of hospitalizations at the end of life will be compared using linear regression models or count regression models (e.g., Poisson, negative binomial) if the linear regression distributional assumptions are violated. The rates of chemotherapy administration (any versus none) at the end of life will be compared using generalized linear models specified with an identity link function and binomial response probability distribution. Additionally, the occurrence of any emergency department visit or any hospitalization at the end of life may be compared using these binomial models. Model-based estimates of the mean or rate with 95% CI in each group and the difference in means or rates between groups and its 95% CI will be reported.

This addendum to the STEP SAP includes detailed clarifications and required modifications that were made to the analysis plan after the SAP had been finalized and signed.

Index	Date	Topic: Description
1	11/21/2023	
Change in scoring method used for Self-Administered Comorbidity Questionnaire (SCQ):
 
This item clarifies how the SCQ scores were calculated such that the range for scores is 0-36.
 
The SCQ includes 13 conditions with 3 yes/no questions (scored 1/0) about each condition. In addition, there are fields for 2 “other” (write in) conditions, each with 3 yes/no questions. The score for each condition ranges from 0-3, and scores for each condition are summed to compute the total SCQ score. We did not include the “other” conditions in the scoring, and we combined responses for osteoarthritis and rheumatoid arthritis into a single “arthritis” condition based on the approach used in the primary SCQ manuscript. Thus, the SCQ scores could range from 0-36.

2	12/21/2023	
Inclusion of week 12 assessments for prognostic understanding (exploratory outcome):
 
This item clarifies that we will use the final post-baseline prognostic understanding assessment for exploratory outcome #4 (i.e., we will use week 12 prognostic understanding if week 24 is missing):
 
 
Patient-reported prognostic understanding at week 24 (or week 12 if week 24 is missing), based on relevant items on the PTPQ, including: 
 
Patient’s primary goal of current cancer care. Responses will be dichotomized based on whether the patient selected “to cure my cancer” versus any of the other options.
 
Patient’s endorsement of the statement “My cancer is curable,” analyzed as “yes” versus “no.”
 
 
 

3	1/5/2024	
Week 24 analysis time point for PC resource utilization (secondary outcome):
 
To align with the primary outcome (evaluated at 24 weeks), we will evaluate secondary outcome #3 in the SAP through week 24:
 
 
PC resource utilization; specifically, the number of outpatient PC visits per patient through week 24, as documented in the EHR.
 

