### *Stepped PC*

Patients randomized to stepped PC were scheduled for an initial visit with a PC clinician within 4 weeks of enrolment. During step 1, further visits with a PC clinician were scheduled at clinically significant points in the patient's illness, including within 4 weeks of (1) a change in cancer treatment (due to either progression or toxicity) or (2) hospital discharge. After each visit, the PC clinician communicated with the oncology clinician(s) either by telephone, email or in person. If a patient missed a scheduled visit or was unable to be scheduled for a PC visit, the PC clinician attempted to contact them by telephone and rescheduled the visit as soon as possible. Patients assigned to stepped PC completed the FACT-L every 6 weeks during the first 18 months of study participation. Those whose scores decreased by  $\geq 10$  points from baseline were 'stepped up' to step 2 and followed the same protocol as those randomized to the early integrated PC arm.

All study participants in both groups surviving greater than 18 months from enrolment were permitted to decrease the frequency of PC visits as per their preference and the discretion of their PC and oncology clinicians.

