## 6. Outcome Measures

Outcome data included self-report questionnaires collected prior to randomization (baseline) and then again at weeks 12, 24, 36 and 48 (with a  $\pm 2$ -week window) (see Table 1), as well as information collected from the EHR.

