**Table 1. Study Questionnaires**

Self-report measure	Baseline	Every 6 weeks	Weeks 12, 24, 36 & 48	Scoring
Demographics	X			n/a
SCQ	X			Range: 0-45 (higher is worse medical condition)
FACT-L	X	X 	X	Range: 0-136 (higher is better QOL)
PHQ-9	X		X	Range: 0-27 (higher is worse depression)
PTPQ	X		X	n/a

Brief Cope	X		X	Range: 2-8 for each facet (higher is more engagement in coping style)
EQ-5D	X		X	VAS Range: 0-100 (higher is better health state)
Support Service Utilization Item			X 	

 Step 1 patients completed FACT-L every 6 weeks for up to 18 months from enrollment.

 Collected only at week 24.

EQ-5D, EuroQol—5 Dimension; FACT-L, Functional Assessment of Cancer Therapy-Lung; PHQ-9, Patient Health Questionnaire-9; PTPQ, Prognosis and Treatment Perceptions Questionnaire; SCQ, Self-administered Comorbidity Questionnaire.

The primary outcome is patient-reported quality of life at 24 weeks from enrollment, as measured by the FACT-L.

The secondary outcomes are:

1. Patient report of patient-clinician communication about EOL care preference using the following item on the PTPQ: “Have you and your doctors discussed any particular wishes you have about the care you would want to receive if you were dying?” analyzed as “yes” versus “no.” The patient’s final assessment will be used.
2. Length of stay on hospice (in days) among patients who die during the study, as documented in the EHR.
3. PC resource utilization; specifically, the number of outpatient PC visits per patient during the study, as documented in the EHR.

The exploratory outcomes are:

1. Rate of change in quality of life from baseline to week 48, as measured by the FACT-L.
2. Cost-effectiveness as assessed by costs relative to quality adjusted life years. **Note:** Plans for the analysis of cost-effectiveness are not described in this SAP.
3. Patient-reported coping strategies at week 24, as measured by eight subscales of the Brief Cope, including subscales measuring emotional support, positive reframing, active coping, acceptance, self-blame, denial, spiritual coping, and behavioral disengagement, as well as higher-order factors reflecting active coping and avoidant coping).
4. Patient-reported prognostic understanding at week 24, based on relevant items on the PTPQ, including:
  - a. Patient’s primary goal of current cancer care. Responses will be dichotomized based on whether the patient selected “to cure my cancer” versus any of the other options.

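### The exploratory 48-week FACT-L slope model has no random slope, so its interval is too narrow if patients' slopes differ, and it does not exclude 6-weekly scores that only the stepped arm has

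*SAP*

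**What the plan says.** The exploratory outcome is "The rate of change in quality of life from baseline to week 48". SAP section 9 (Exploratory Outcomes) fits it with a linear mixed model, estimated by maximum likelihood: "This model will utilize FACT-L scores at each timepoint". The fixed effects are group, linear time, their interaction and the stratification factors, "as well as random intercepts for each patient". The slope difference is reported with a 95% CI.

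The weeks are not listed. In the same section, the mixed model that supports the primary outcome does list them: "This model will utilize FACT-L scores at baseline, week 12, and week 24".

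Two FACT-L schedules exist. SAP section 6 says outcome questionnaires were "collected prior to randomization (baseline) and then again at weeks 12, 24, 36 and 48", which applies to both arms. SAP Table 1 also has an every-6-weeks column, marked for FACT-L alone, with the footnote "Step 1 patients completed FACT-L every 6 weeks for up to 18 months from enrollment". Protocol section 5.3.1 and protocol Table 1 likewise tie this schedule to step 1. SAP section 5 words it more widely: "Patients assigned to stepped PC completed the FACT-L every 6 weeks during the first 18 months of study participation". None of the three SAP addendum items says whether the 6-weekly scores enter the slope model.

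**The concern.** There are two weaknesses in one model.

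**Covariance.** A random intercept lets patients differ in level but not in rate of change. In advanced lung cancer some patients hold steady while others fall quickly. If slopes vary, the model treats that variation as independent visit-to-visit noise and understates the standard error of the slope difference.

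**Data.** No early integrated patient has a scheduled score at weeks 6, 18, 30 or 42. In the stepped arm, a fall of 10 or more points from baseline ends step 1 permanently (protocol section 5.3.1). Under the step 1 wording it therefore also ends the 6-weekly forms, so the number of scores a stepped patient contributes depends on the outcome being modelled. Maximum likelihood tolerates selection on observed scores only when the mean and covariance models are right, and this covariance may well not be.

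At stake is an exploratory estimate and interval on the trial's primary instrument, which could look more precise than it is and could be shifted by one arm's measurement schedule.

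**Working it through.** **Figures in the plan.** The documents give no precision, power or bias figure for the slope. The nearest FACT-L figure is 188 per group at week 24 (SAP section 7). It reproduces: 2 × 17.5² × (1.645 + 0.842)² / 4.5² = 187.0, rounded up to 188. It says nothing about slopes.

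**Inputs.** From the documents: 255 per arm, the visit weeks, the 10-point step-up rule, and the prior usual-care trial's 30% plus 11% with such a fall by week 24. Assumed, because the documents do not give them: between-patient slope SD τ of 0.15 to 0.45 points/week and residual SD σ of about 6 to 12. Over 48 weeks these τ values mean that patients' changes vary with an SD of 7.2 (0.15 × 48) to 21.6 points (0.45 × 48).

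**Step 1: interval width on shared visits.** Take complete data at weeks 0, 12, 24, 36 and 48, with mean week 24.

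- Σ(t − 24)² = 576 + 144 + 0 + 144 + 576 = 1,440.
- True variance of one patient's fitted slope: σ²/1,440 + τ² = (σ² + 1,440τ²)/1,440.
- The random-intercept model pools slope variation into residual variance over 4 degrees of freedom per patient: σ² + 1,440τ²/4 = σ² + 360τ². It therefore reports (σ² + 360τ²)/1,440.
- True over reported variance: R = (σ² + 1,440τ²)/(σ² + 360τ²). Non-coverage of a 95% CI is 2 × [1 − Φ(1.96/√R)].

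With σ = 8:

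| τ | R | √R | 1.96/√R | Non-coverage |
|---|---|---|---|---|
| 0.15 | 96.4/72.1 = 1.34 | 1.16 | 1.70 | 9% |
| 0.30 | 193.6/96.4 = 2.01 | 1.42 | 1.38 | 17% |
| 0.45 | 355.6/136.9 = 2.60 | 1.61 | 1.22 | 22% |

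Simulation of the SAP model on shared visits gave about 10 to 21% over the same range of τ, and about 17% at τ = 0.30. At τ = 0.30 the half-width reported over 48 weeks is 1.96 × 48 × √(96.4/1,440) × √(2/255) = 2.2 points. The correct half-width replaces 96.4 with 193.6 and is 3.1 points.

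**Step 2: effect of the extra scores.** With random intercepts only, each patient's slope is weighted roughly by the spread of that patient's visit times. A stepped patient with all nine scores has Σ(t − 24)² = 2,160. One who steps up at week 6 or 12 keeps weeks 0, 6, 12, 24, 36 and 48 (mean 21), giving 441 + 225 + 81 + 9 + 225 + 729 = 1,710. Patients who hold up therefore count more, by 2,160/1,710 = 1.26, and only in the stepped arm.

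Simulated slope difference (stepped minus early, points over 48 weeks, truth 0; 400 trials per row; intercept SD 14; 50% attrition by week 48; 33 to 45% stepped up by week 24):

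| Setting | With 6-weekly scores | Shared visits only |
|---|---|---|
| Linear mean, τ = 0, independent errors | −0.05 | −0.07 |
| Linear, τ = 0.15 | +0.18 | −0.05 |
| Linear, τ = 0.30 | +0.77 | −0.02 |
| Linear, τ = 0.45 | +1.71 | +0.01 |
| 4-point dip at week 6, τ = 0.30 | +2.39 | −0.02 |
| 4-point rise at week 6, τ = 0.30 | −0.88 | −0.02 |
| 8-point rise at week 6, τ = 0.30 | −2.54 | −0.02 |

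Monte Carlo standard errors are 0.06 to 0.12. Over all settings tried, the near-linear bias runs from about +0.2 to +1.5, with single runs just outside at +0.15 and +1.7. Other early-rise patterns gave reversals as small as −0.4. At τ = 0.30 the extra scores raise non-coverage from about 17% to 21–24%, so most of the excess comes from the missing random slope.

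**Step 3: effect of a random slope.** In a small check (12 trials, τ = 0.45, all scores), the shift from the shared-visit estimate fell from 1.90 (SE 0.17) to 0.28 (SE 0.23) once a random slope was added. This is indicative only.

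**The case against.** The case against is substantial.

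- **The wording probably means the shared visits.** SAP section 6 introduces outcome questionnaires as baseline and weeks 12, 24, 36 and 48, and protocol section 5.3.1 gives the 6-weekly FACT-L a different job, deciding who steps up. A reader might infer that the SAP plans to feed one-arm scores into the slope model. The documents do not say so; they only fail to exclude it. The ambiguity stands, because section 6 points to Table 1, which carries the 6-weekly column.
- **The selection is not absolute.** A reader might infer that the extra scores exist only for patients who have not declined. That is too strong: the week-6 form is due from every stepped patient, and the score that triggers step-up is itself recorded. If SAP section 5 describes what was done, collection did not stop at step-up, and mainly unequal visit density remains.
- **The direction is not fixed.** A reader might infer a certain tilt toward stepped PC. The bias is about zero when slopes do not vary and errors are independent, and an early rise reverses it.
- **The outcome is exploratory.** No test threshold is planned, so the non-coverage figures describe interval quality, not a planned decision error. The primary regression does not use this model. Its mixed-model sensitivity analysis names baseline, week 12 and week 24, so the extra scores cannot enter. That model also has random intercepts only, but its week-24 contrast is a different quantity and is not assessed here.

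None of this answers the covariance point, which holds on the shared visits alone.

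**Conclusion.** The point holds in a limited form. If patients' slopes differ, the stated random-intercept model gives a 95% CI for the slope difference that is too narrow. Non-coverage is about 10 to 21% rather than 5% for assumed slope SDs of 0.15 to 0.45 points/week; with no slope variation the problem disappears. This part does not depend on how the visit wording is read.

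Separately, the model does not exclude scores that only one arm has and whose number can depend on the outcome. If they were used, the likely bias is about +0.2 to +1.5 points over 48 weeks toward stepped PC with a near-linear mean. Its size and sign rest on assumptions about slope variation and the shape of the mean that the documents cannot settle. The documents do not support saying that the bias is planned or that its direction is certain. The consequence is confined to an exploratory result.

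**What to change.** Make three changes, which could be a further item in the SAP addendum:

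1. In SAP section 9 (Exploratory Outcomes), state that the slope model uses FACT-L at baseline and weeks 12, 24, 36 and 48 in both groups, and that the additional 6-weekly assessments are excluded.
2. Add a random slope for time to that model, or use an unstructured covariance over the five visits. Name a simpler fallback covariance in case the model does not converge.
3. Reconcile the SAP section 5 description of who completed the 6-weekly FACT-L with the Table 1 footnote and protocol section 5.3.1.

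The cost is a few sentences, a somewhat wider CI for the slope difference, and the need for the fallback. No shared-visit data are lost.
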